8.4. Data Sources

This study will be conducted using health plan claims data held by Data Partners that participate in the FDA's Sentinel System, including CVS Health (Aetna), HealthCore (Anthem), Humana, and Optum. These Data Partners typically update their quality-checked data 3 to 4 times per year, although some are updating more frequently with fresher data (ie, shortened data lags) to support FDA-initiated COVID-19 analyses. The study will use the most up-to-date standardized and curated data source available within each Data Partners, leveraging the Sentinel Common Data Model (SCDM). These databases capture longitudinal information on vaccines, medical products (dispensed prescriptions, vaccines administered), inpatient and outpatient diagnoses, inpatient and outpatient treatments and procedures, based on billing codes as well as laboratory results.

The average enrollment length for patients across data sources participating in the Sentinel System is similar to other claims databases of members with medical and pharmacy coverage; about 25% of patients have over 3 years of enrollment, and patients with chronic conditions such as diabetes and older members typically have longer than average enrollment periods within these databases. All study data will be accessed with procedures compliant with US subject confidentiality requirements, including the Health Insurance Portability and Accountability Act of 1996 (HIPAA). Where appropriate, as required by local regulations, this study will be undertaken only after the IEC/IRB has given full approval of the final protocol, any applicable amendments, and the sponsor has received a copy of this approval.

8.4.1. CVS Health (Aetna)

Aetna, a CVS Health company, is one of the nation's leading healthcare benefits companies, serving 38 million people. Aetna became an FDA Sentinel Data Partner in 2010. Aetna's SCDM captures longitudinal information on dispensed prescriptions, inpatient and outpatient diagnoses, inpatient and outpatient treatments and procedures, and laboratory results. As of December 2020, there were approximately 35 million unique individuals available for research.

8.4.2. HealthCore

HealthCore, Inc., a participant in Sentinel since 2008, is a significant contributor to the Sentinel Collaboration and Sentinel Distributed Database. The HealthCore Integrated Research Database (HIRD) is a broad, clinically rich, and geographically diverse data spectrum of longitudinal medical and pharmacy claims data from commercially-insured health plan members across the US. Member's enrollment, medical care (professional and facility claims), prescription drug use, laboratory test result data, and healthcare utilization, all of which may be tracked for health plan members in the database dating back to January 2006. As of February 2021, there were 79 million unique individuals with medical coverage and approximately 60 million with medical and pharmacy coverage available for research.

8.4.3. Humana

Humana Healthcare Research Inc. (HHR) is a wholly owned health economics and outcomes research subsidiary of Humana Inc. HHR focuses on conducting research on various topics, including treatment effectiveness, drug safety, adherence, medical and pharmacy benefit design, disease management programs, and other healthcare services based on the Humana health plan member population. HHR has been an active collaborator and Data Partner in the FDA Sentinel System and several large national distributed research networks. Humana databases represent geographic coverage for the entire US population and represent over 27 million lives.

8.4.4. Optum Research Database

The Optum Research Database is a proprietary research database that contains eligibility data and medical claims and includes health plan members who are geographically diverse across the US and comprise approximately 3% to 4% of the US population. Optum has curated and quality-checked data formatted to the SCDM available for use and is a longtime participant in the Sentinel System.

8.5. Study Size

8.5.1. SCRI

Table 2 shows the statistical power that can be obtained for a range of relative risks and a range of sample sizes. For example, a sample size of 100 will allow the detection of a relative risk equal to or greater than 2 with 93% statistical power.

Table 2: Detectable Relative Risk and Statistical Power for SCRI Design

Relative Risk	Number of Events in Risk and Control Period	Power
1.5	20	0.142
2	20	0.320
2.5	20	0.495
3	20	0.638
1.5	50	0.292
2	50	0.667
2.5	50	0.881
3	50	0.963
1.5	100	0.519
2	100	0.926
2.5	100	0.994
3	100	1.000
1.5	150	0.692
2	150	0.987
2.5	150	1.000
3	150	1.000
1.5	200	0.812
2	200	0.998
2.5	200	1.000
3	200	1.000

Source: Musondo, 2006.

8.5.2. Cohort

Subject to the feasibility assessment, a minimum target sample size of 100,000 individuals in the exposed cohort will be included in the study. Table 3 shows the probabilities that the upper limit of the 95% CI around the observed relative risk will be less than 1.5, 2.0, 2.5, or 3.0 for various study sizes, incidence rates, and values of the actual relative risk in the population. These calculations assume a matching ratio exposed/comparator of 1:4.

For example, assuming a total of 100,000 individuals in the exposed cohort and 400,000 in the comparator cohort, each followed for a 60-day risk window, if the incidence rate of the outcome is 50 per 100,000 person-years in the comparator cohort and the actual relative risk in the population is 1.0, the probability that the upper limit of the 95% CI of the observed relative risk will be below 3.0 is 0.805. For the same study size and rate but assuming the actual relative risk in the population is 1.2, the probability that the upper limit of the 95% CI of the observed relative risk will be below 3.0 is 0.714.

Table 3: Probability that upper bound of 95% CI will be below specified relative risks

Actual RR in	Number of Exposed	Incidence Rate in Comparator Individuals (Cases per 100,000 Person-	Upper 95% Bound of Relative Risk					
Population	Individuals	years)	1.5	2	2.5	3		
1.0	50,000	1	0.032	0.037	0.042	0.047		
		10	0.051	0.081	0.112	0.143		
		50	0.110	0.241	0.383	0.513		
		100	0.179	0.428	0.652	0.805		
	100,000	1	0.035	0.044	0.052	0.059		
		10	0.067	0.122	0.182	0.242		
		50	0.179	0.428	0.652	0.805		
		100	0.312	0.711	0.914	0.979		
	200,000	1	0.040	0.054	0.068	0.081		
		10	0.096	0.202	0.318	0.429		
		50	0.312	0.710	0.914	0.979		
		100	0.548	0.945	0.997	1.000		
1.2	50,000	1	0.029	0.034	0.039	0.044		
		10	0.039	0.065	0.093	0.123		
		50	0.064	0.167	0.298	0.431		
		100	0.089	0.290	0.525	0.714		
	100,000	1	0.031	0.039	0.047	0.054		
		10	0.046	0.092	0.146	0.203		
		50	0.089	0.290	0.525	0.714		
		100	0.138	0.512	0.816	0.946		
	200,000	1	0.033	0.047	0.060	0.073		
		10	0.058	0.142	0.248	0.358		
		50	0.138	0.512	0.816	0.946		

CONFIDENTIAL – FOIA Exemptions Apply in U.S.

Actual RR in	Number of Exposed	Incidence Rate in Comparator Individuals (Cases per 100,000 Person-	Upper 95% Bound of Relative Risk				
Population	Individuals	years)	1.5	2	2.5	3	
		100	0.233	0.804	0.981	0.999	
1.4	50,000	1	0.026	0.032	0.037	0.041	
		10	0.029	0.051	0.077	0.105	
		50	0.035	0.111	0.223	0.350	
		100	0.039	0.179	0.395	0.605	
	100,000	1	0.027	0.035	0.043	0.050	
		10	0.031	0.068	0.115	0.167	
		50	0.039	0.179	0.395	0.605	
		100	0.047	0.313	0.668	0.883	
	200,000	1	0.027	0.040	0.052	0.065	
		10	0.033	0.097	0.187	0.290	
		50	0.047	0.313	0.668	0.883	
		100	0.060	0.549	0.923	0.994	

Source: Rothman, 2015

Note: Calculations assume that each individual contributes a 60-day risk window.

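### Table 3's large-sample formula cannot go below 0.025, so its cells for very rare outcomes print 0.026–0.081 where the true probability is effectively zero

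*Protocol*

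**What the plan says.** Protocol section 8.5.2 describes Table 3 as giving "the probabilities that the upper limit of the 95% CI around the observed relative risk will be less than 1.5, 2.0, 2.5, or 3.0". The grid crosses three exposed-cohort sizes with four comparator rates and three assumed true RRs. The stated conditions are "These calculations assume a matching ratio exposed/comparator of 1:4" and, in the table note, "Calculations assume that each individual contributes a 60-day risk window". The target is "a minimum target sample size of 100,000 individuals in the exposed cohort will be included in the study", subject to the feasibility assessment.

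The first worked example takes 100,000 exposed, 50 per 100,000 person-years and true RR 1.0, and reports that "the probability that the upper limit of the 95% CI of the observed relative risk will be below 3.0 is 0.805". The second changes the true RR to 1.2 and reports 0.714.

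At 1 per 100,000 person-years and RR 1.0, the rows for 50,000 and 200,000 exposed read "50,000 1 0.032 0.037 0.042 0.047" and "200,000 1 0.040 0.054 0.068 0.081". Over all three true RRs, the 36 cells at this rate run from 0.026 to 0.081. The source is cited as an epidemiologic spreadsheet. No formula, expected event count or warning about small numbers is given.

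**The concern.** At 1 per 100,000 person-years the cohort would usually see no exposed event at all, and an upper confidence limit below 3, let alone 1.5, should then be almost impossible. Yet the printed cells level off just above 0.025 instead of falling towards zero. That is what a normal approximation does when used outside its range.

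Table 3 is the protocol's only statement of how well the cohort design can exclude a raised risk. Its low-rate rows are the ones a reader would consult for rare AESIs. Table 1 lists rates below 1 per 100,000 at the low end for Guillain-Barré syndrome, transverse myelitis, cerebral venous thrombosis and disseminated intravascular coagulation, and a single rate of 0.55 for acute hepatic failure.

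**Working it through.** **Inputs (section 8.5.2 and Table 3).** N exposed = 50,000, 100,000 or 200,000; 4N comparators; 60 days each; comparator rate r = 1, 10, 50 or 100 per 100,000 person-years; true RR = 1.0, 1.2 or 1.4; bound b = 1.5, 2.0, 2.5 or 3.0; two-sided 95% interval.

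**Step 1: reproduce the table.** Expected events are A = N × (60/365.25) × r × RR (exposed) and C = 4N × (60/365.25) × r (comparator). The formula is

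P = Φ( ln(b/RR) / √(1/A + 1/C) − 1.96 ).

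- N = 100,000, r = 50, RR = 1.0, b = 3.0: A = 8.214, C = 32.854, SE = √(0.1217 + 0.0304) = 0.390; 1.0986/0.390 − 1.96 = 0.856; Φ = 0.804 (printed 0.805).
- N = 200,000, r = 1, RR = 1.0, b = 3.0: A = 0.329, C = 1.314, SE = 1.951; 1.0986/1.951 − 1.96 = −1.397; Φ = 0.081 (printed 0.081).

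The formula matches all 144 cells to within 0.0012.

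**Step 2: the floor.** As A and C shrink, SE grows without limit and the first term tends to 0. The smallest bound (1.5) exceeds the largest true RR (1.4), so that term is always positive and P stays above Φ(−1.96) = 0.025. The smallest printed cell is 0.026 (RR 1.4, 50,000 exposed, rate 1, bound 1.5).

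**Step 3: direct calculation on the same inputs.** Let a and c be independent Poisson counts with means A and C. Given n = a + c, the upper limit lies below b when P(X ≤ a) < 0.025 for X ~ Binomial(n, b/(b+4)); mid-P counts only half of P(X = a). Sum the Poisson probabilities of all qualifying (a, c).

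With no exposed events the exact condition is (4/(b+4))^c < 0.025.

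- b = 3.0: (4/7)^6 = 0.035 and (4/7)^7 = 0.020, so at least 7 comparator events are needed (6 with mid-P).
- b = 1.5: (4/5.5)^11 = 0.030 and (4/5.5)^12 = 0.022, so at least 12 are needed (10 with mid-P).

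At 100,000 exposed, rate 1 and RR 1.0, C is only 0.66. About 44% of such studies would have no event in either group, and about 85% none in the exposed group.

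**Results, RR 1.0, bound 3.0:**

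| Exposed | Rate per 100,000 PY | A / C | Printed | Exact | Mid-P |
|---|---|---|---|---|---|
| 50,000 | 1 | 0.08 / 0.33 | 0.047 | 0.00000006 | 0.000001 |
| 100,000 | 1 | 0.16 / 0.66 | 0.059 | 0.000005 | 0.00005 |
| 200,000 | 1 | 0.33 / 1.31 | 0.081 | 0.0003 | 0.0017 |
| 50,000 | 10 | 0.82 / 3.29 | 0.143 | 0.023 | 0.053 |
| 100,000 | 10 | 1.64 / 6.57 | 0.242 | 0.145 | 0.213 |
| 100,000 | 50 | 8.21 / 32.85 | 0.805 | 0.845 | 0.878 |

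Over all 36 rate-1 cells (A from 0.08 to 0.46) the maximum is 0.0003 exact and 0.0017 mid-P. Log-scale Wald limits, with or without 0.5 added to the counts, also stay at or below 0.0017, so this result does not depend on the interval.

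For RR 1.0 and bounds 1.5/2.0/2.5/3.0, the rate-10 rows are:

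- 50,000 exposed: printed 0.051/0.081/0.112/0.143; exact 0.0001/0.001/0.009/0.023; mid-P 0.001/0.009/0.023/0.053.
- 100,000 exposed: printed 0.067/0.122/0.182/0.242; exact 0.007/0.028/0.079/0.145; mid-P 0.026/0.077/0.139/0.213.

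The second worked example (RR 1.2) is 0.714 printed, 0.728 exact and 0.774 mid-P.

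**The case against.** **The arithmetic is sound.** That stands: every cell follows from the stated inputs. The fault is a large-sample formula used with well under one expected exposed event, without saying so.

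**No decision rests on these cells.** This also stands. The 100,000 minimum is not derived from Table 3, and both worked examples use a rate of 50. A reader might infer that the study size or the whole table is discredited. The documents do not support that: both examples are slightly conservative, as are some other higher-count cells (at 8.2 expected exposed events, RR 1.0, bound 2.5: printed 0.652, exact 0.674, mid-P 0.723). A printed 3–8% already signals poor precision.

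**The rows have limited reach.** A reader might infer that the primary analysis of the rarest AESIs is affected. It is not. The AESIs with listed rates at or below 1 per 100,000 are acute. Their primary design is the self-controlled risk interval, which has its own Table 2, and the cohort is only their sensitivity analysis. Table 1 also gives ranges, some with much higher upper ends (Guillain-Barré syndrome up to 23). Among cohort-primary outcomes, multiple sclerosis has the lowest listed rate, 2 per 100,000 over 365 days. With full follow-up and RR 1.0, 100,000 exposed give about 2 expected exposed events. That equals 2 × 365/60 ≈ 12 per 100,000 over 60 days, so it is nearest the rate-10 rows.

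**The rate-10 corrections depend on the interval.** This stands. Section 8.7.1.2 leaves the estimation method to the SAP, and for 100,000 exposed, RR 1.0 and bound 3.0, mid-P is only 0.03 below the printed value. Exact and mid-P both lie below print throughout the 50,000 and 100,000 rows at that rate, but no single correct figure is fixed by this document.

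**Conclusion.** The point holds as a limited one. On Table 3's own 60-day, 1:4 inputs, the 36 cells at 1 per 100,000 person-years overstate a probability that is effectively zero: 0.026–0.081 printed, at most 0.0017 under any interval tried. The rate-10 rows at 50,000 and 100,000 exposed are overstated by an amount that varies with the interval.

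The calculation assumes independent Poisson counts, full 60-day follow-up and no allowance for matching, which are the table's own simplifications. The practical effect is mainly on how the cohort sensitivity analyses of very rare acute AESIs are read and, through the rate-10 rows, on low-rate cohort-primary outcomes such as multiple sclerosis.

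A reader might take the 15% (exact) to 21% (mid-P) figure as a general ceiling at 10 per 100,000. It applies only to 100,000 exposed, true RR 1.0, bound 3.0 and 60 days. A 365-day outcome at the same rate would yield about six times the events.

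**What to change.** Recompute all of Table 3 from the Poisson distribution of the two event counts, using one stated interval (exact conditional or mid-P). Add expected exposed and comparator events to each row. State in section 8.5.2 that outcomes with fewer than about 2 expected exposed events cannot usefully exclude RR 3. If a ceiling such as 15–21% at 10 per 100,000 is quoted, attach its conditions: 100,000 exposed, true RR 1.0, bound 3.0, 60 days.

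The cost is a few lines of code and a replaced table. The low-rate figures become less favourable and some higher-count figures slightly more so. No change to design or data is needed.

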Cohorts will be defined utilizing existing secondary healthcare data sources. One year of medical and pharmacy insurance enrollment prior to the reference date will be required to determine whether individuals meet the study criteria and to define baseline characteristics. Data on the occurrence of AESI will be extracted within the 1 year after the reference date.

Figure 2: Cohort Study Design

[figure not shown]
Ad26.COV2.S exposed cohort

Outcome-specific follow-up periods after vaccine receipt

Comparator BNT162b2 exposed cohort

Outcome-specific risk periods after dose 1 for outcomes with risk windows \leq 21 days

Comparator BNT162b2 exposed cohort

If vaccine dose 2 is received during the outcome-specific risk period after dose 1, the risk periods of dose 1 and dose 2 are concatenated into a single risk period, and follow-up ends after the duration of the outcome-specific risk period following dose 2. If vaccine dose 2 is not received, the outcome-specific risk window extends the full length from dose 1.

Outcome-specific risk windows:

- 2 days: anaphylaxis.
- 14 days: generalized convulsion, arrhythmia, acute kidney failure, acute hepatic failure.
- 21 days: cardiac inflammatory disorders, including myocarditis and pericarditis, and sensorineural hearing loss.

- 28 days: microangiopathy, disseminated intravascular coagulation, DVT, pulmonary embolism, hemorrhagic and non-hemorrhagic stroke, acute myocardial infarction, coronary artery disease (including acute myocardial infarction), heart failure, stress cardiomyopathy, venous thrombosis composite endpoint, arterial thrombosis composite endpoint, stroke composite endpoint.
- 42 days: encephalitis (including acute demyelinating encephalomyopathy and meningoencephalitis), Guillain Barré Syndrome, Bell's palsy, immune thrombocytopenia, thrombocytopenia, transverse myelitis.
- 365 days: autoimmune thyroiditis, acute aseptic arthritis, multiple sclerosis (including optic neuritis), Type 1 diabetes mellitus.

Note that follow-up time for the primary analysis will end upon receipt of a booster dose of Ad26.COV2.S or a booster dose of any COVID-19 vaccine.

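### Table 3 gives cohort precision for a 60-day risk window that no AESI has, so its probabilities describe no planned cohort analysis

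*Protocol*

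**What the plan says.** Section 8.5.2 illustrates the minimum target cohort size with 100,000 exposed and 400,000 comparator individuals, "each followed for a 60-day risk window". For a comparator rate of 50 per 100,000 person-years and a true relative risk of 1.0, it states that "the probability that the upper limit of the 95% CI of the observed relative risk will be below 3.0 is 0.805"; with a true relative risk of 1.2, "the probability that the upper limit of the 95% CI of the observed relative risk will be below 3.0 is 0.714". The matching is fixed too: "These calculations assume a matching ratio exposed/comparator of 1:4". The note under Table 3 extends the window to the whole table: "Calculations assume that each individual contributes a 60-day risk window".

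The risk windows are set in Section 7, in Figure 2 (Section 8.1.1.2) and in Table 1 (Section 8.3.4.2): 0-2 days for anaphylaxis, then 1-14, 1-21, 1-28 and 1-42 days for the other acute AESIs. The last group in Figure 2 reads "365 days: autoimmune thyroiditis, acute aseptic arthritis, multiple sclerosis (including optic neuritis), Type 1 diabetes mellitus". Sections 8.1.1 and 8.1.2 make the cohort design primary for the non-acute events, which are those four AESIs. Section 8.7.5.3 uses it as a sensitivity analysis for acute events, whose primary analysis is the SCRI, sized separately in Table 2. Elsewhere in the protocol, 60 days is only the boundary between acute and non-acute events.

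**The concern.** Table 3 is the protocol's only statement of what a cohort of 100,000 exposed and 400,000 comparators can rule out. Its probabilities depend on the expected event counts, which are proportional to the length of follow-up. Sixty days is longer than every acute window and much shorter than the non-acute one, so the table can mislead in both directions:

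- A reader may think the primary analysis of the 365-day AESIs is weaker than it is.
- A reader may think the sensitivity cohort analysis of a rare acute AESI is more informative than it is, and take a wide, inconclusive interval as support for the SCRI result.

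Amendment 2 reduced the scope of the study because of low vaccine uptake, so the precision the cohort can deliver is a live question.

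**Working it through.** **Inputs.** From Section 8.5.2: N = 100,000 exposed, ratio 1:4, rate 50 per 100,000 person-years in comparators, true RR 1.0 (or 1.2), two-sided 95% interval. From Figure 2 and Table 1: the risk windows. From Section 8.3.5.2: BNT162b2 doses are 21 days apart, and the two risk periods are joined when dose 2 falls within the first.

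**Formula.** With d1 and d0 the days of follow-up per exposed and per comparator individual:

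- a = N × (d1/365) × rate × RR (expected exposed events)
- b = 4N × (d0/365) × rate (expected comparator events)
- SE = √(1/a + 1/b)
- P(upper limit < U) = Φ[ln(U/RR)/SE − 1.96]

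**Reproducing the protocol.** With d1 = d0 = 60 and RR = 1.0, a = 8.22, b = 32.88 and SE = 0.390. For U = 3.0, P = Φ(1.0986/0.390 − 1.96) = Φ(0.857) = 0.804 (stated 0.805). At RR = 1.2, a = 9.86, SE = 0.363 and P = 0.714 (stated 0.714). All 144 cells of Table 3 reproduce with a largest difference of 0.0009, so the method is identified and the arithmetic is sound.

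**Acute windows** (sensitivity cohort analysis; RR 1.0, U = 3.0, stated 0.805):

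| Window (days) | a | P, equal windows | P, comparator window 21 days longer |
|---|---|---|---|
| 3 (days 0-2) | 0.41 | 0.09 | not applicable |
| 14 | 1.92 | 0.27 | not applicable |
| 21 | 2.88 | 0.38 | 0.42 |
| 28 | 3.84 | 0.49 | 0.52 |
| 42 | 5.75 | 0.65 | 0.68 |

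The last column uses d0 = 42, 49 and 63 days. It assumes that every comparator receives dose 2 at day 21. For the 21-day window that is the boundary case, so 0.42 is an upper value.

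**Dependence on the rate.** At 28 days with equal windows, P(upper < 3.0) is 0.60 at 66 per 100,000 person-years (the lower end of Table 1 for deep vein thrombosis), 0.81 at 108 (the arterial thrombosis composite) and above 0.999 at 812 (the lower end for heart failure, a rate estimated at age 65 and over).

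**365-day AESIs** (primary cohort analysis; RR 1.0, 50 per 100,000 person-years). The protocol gives no mean follow-up after censoring, so the means of 120, 180 and 240 days are assumptions, taken as equal in both cohorts:

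| Mean follow-up (days) | a / b | P(upper < 1.5) | P(upper < 2.0) |
|---|---|---|---|
| 60 (as in Table 3) | 8.2 / 32.9 | 0.179 | 0.428 |
| 120 | 16.4 / 65.8 | 0.31 | 0.71 |
| 180 | 24.7 / 98.6 | 0.44 | 0.87 |
| 240 | 32.9 / 131.5 | 0.55 | 0.94 |
| 365 (no censoring) | 50 / 200 | 0.73 | 0.99 |

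**Direction over the whole table.** Before rounding, a full 365 days raises all 144 cells, and each acute window lowers all 144, including 42 days with a 63-day comparator window. At three decimals, at most two cells per scenario are unchanged.

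**Sparse rows.** At 100,000 exposed, 60 days and 10 per 100,000 person-years, a = 1.64. The stated 0.242 becomes 0.145 with an exact conditional interval and 0.213 with its mid-P version. At 1 per 100,000 person-years (a = 0.16), the stated 0.035-0.059 is essentially zero with the exact interval. In the worked example, the exact value is 0.845, above the stated 0.805.

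**The case against.** The strongest defence is that nothing is miscalculated: the window is disclosed in the text and under the table. Because only expected counts matter, a reader can rescale, at least with equal windows: 14 days at 50 per 100,000 person-years is 60 days at about 12 (50 × 14/60), and 365 days at 10 is 60 days at about 61 (10 × 365/60). This stands as far as it goes. The fault lies in the input, and a precision statement should not leave every planned analysis to be rescaled by the reader.

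It can also be said that little hangs on the table. The 100,000 is a minimum target subject to feasibility, no formal hypothesis is specified, and Table 3 drives no decision rule. For the primary analyses the mismatch is conservative whenever mean follow-up exceeds 60 days; for acute events it touches only a sensitivity analysis. All of this stands and lowers the severity.

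Three stronger readings are tempting, and the documents do not support them:

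- **That every figure in Table 3 is wrong.** The figures are right for 60 days.
- **That the acute cohort analysis usually cannot exclude a relative risk of 3.** That depends on the rate: it fits rare AESIs with short windows, but not those with the higher Table 1 rates.
- **That 0.99 is the precision of the primary non-acute analysis.** That needs a full year from everyone, whereas Section 8.3.5.2 censors at booster, change of brand, disenrollment, death and end of data.

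The exact-interval point is partly a choice of method, which Section 8.7.1.2 leaves to the SAP.

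**Conclusion.** The point holds as a mismatch between a disclosed assumption and the protocol's own risk windows. Table 3 and its example describe no planned cohort analysis.

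For acute AESIs at 50 per 100,000 person-years, the stated 0.805 is too high for every window. The shortfall runs from about 0.12-0.15 at 42 days to about 0.71 at 3 days, in the sensitivity analysis only. For the 365-day AESIs, the stated 0.428 is too low by about 0.28 to 0.52 at assumed means of 120 to 240 days, and by about 0.56 at most, with no censoring. The direction for these AESIs rests on mean follow-up above 60 days, which the protocol does not state. All these differences use the protocol's own normal approximation, which is unreliable where very few exposed events are expected.

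This should be fixed, but it does not threaten the design.

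**What to change.** Replace Table 3 and the worked example with rows for the protocol's own windows:

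- For acute AESIs, use 3, 14, 21, 28 and 42 days, with the longer comparator window wherever dose 2 falls within the risk period. Label these rows as the precision of the sensitivity cohort analysis.
- For the four 365-day AESIs, show a stated range of mean follow-up after censoring, label full 365-day follow-up as the best case, and present these rows as the precision of the primary non-acute analysis.
- Note that the normal approximation is unreliable in rows with very few expected exposed events, or compute those rows with the interval method the SAP will specify.

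The cost is recomputing one table and rewriting one paragraph. No data, design change or new analysis is needed. The acute figures will look less favourable, and the 365-day figures more favourable if mean follow-up exceeds 60 days.
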